### **Additional Outcomes**

The *Life Events Checklist* (LEC; Gray, Litz, Hsu, & Lombardo, 2004) is a 17-item self-report measure for potentially traumatic events in the respondent's lifetime. The LEC assesses exposure to 16 events plus one item assessing any other extraordinarily stressful event. The respondent checks whether they (a) directly experienced, (b) witnessed, (c) learned about, (d) are not sure, and (e) does not apply to them. The LEC has demonstrated adequate reliability and validity. The LEC is administered at baseline assessment only.

The *Moral Injury Outcome Scale* (MIOS; Litz et al., 2020) is a 15-item self-report measure of moral injury. Respondents indicate how much they would agree with certain statements (e.g., “I feel like I don’t deserve a good life” and “I have lost faith in humanity”) over the past month. Agreement is indicated on a 5-point Likert scale ranging from 0 (“Strongly disagree”) to 2 (“Neither agree or disagree”) to 4 (“Strongly agree”). Possible scores range from 0 to 60, with higher scores indicating greater severity of moral injury. The MIOS is administered at baseline and follow-up.

**Update Note:** Due to further work on validating the MIOS, one item was removed resulting in a 14-item self-report measure of moral injury.

## **Adverse Events**

No severe adverse events have been reported of previously used versions of ESTAIR with people with complex trauma, including in randomised controlled trials (Cloitre et al, 2010). However, we wish to improve the recording and reporting of adverse effects of psychological interventions and have therefore developed a robust protocol for assessing and managing any such risk, which will be completed at end of treatment and at follow-up. The Adverse Events Questionnaire (AEQ; Hutton et al., 2015) was initially developed to investigate adverse effects of a psychosis-specific intervention and was adapted for the present study by removing any psychosis-specific items.

The AEQ used in the present study consists of 25 items (e.g., worsening of mental state, heightened stigma, increased medication use), which are responded to on a 5-point scale ranging from “Not at all” to “Very much”. All participants completing the ESTAIR intervention will complete the trial-completer, patient-rated version of the AEQ. To improve on the reporting of adverse events, participants who withdraw from the study will be asked to complete the early-withdrawal version of the AEQ together with the therapist.

Using an approach applied previously (adapted from Klingberg et al., 2012), we will define serious adverse events as (i) death by suicide; (ii) suicide attempt; (iii) suicidal crisis without attempt; (iv) severe symptom exacerbation (increase of 2 standard deviations or more on the patient or researcher-rated ITQ. Non-severe adverse events will be defined as a score of  $\geq 3$  (agree ‘quite a lot’ or ‘a lot’) on any item on the AEQ (Hutton et al., 2015).

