## OUTCOME MEASURES

Outcomes are as follows: **(i)** Retention & data completion rates at weeks 25 weeks post-treatment and 12-week follow-up, on the primary outcome; International Trauma Questionnaire (Cloitre et al., 2018) and secondary outcomes: PHQ Depression (Kroenke et al., 2001), GAD Generalised Anxiety (Spitzer et al., 2006), AUDIT Substance Misuse (Saunders et al., 1993), and PHQ-15 Medically Unexplained Symptoms (Kroenke et al., 2002) **(ii)** 12-month recruitment rate; **(iii)** participant & clinical staff views on trial & intervention acceptability and suggested changes. Baseline information on demographics including age, gender, marital status etc., will be gathered to characterise the sample.

A range of assessments will be administered by the research assistant to test the acceptability of primary (PTSD and CPTSD) (i.e. ITQ) and secondary outcomes (depression, anxiety, alcohol use, and somatisation) (e.g. GHQ-12, AUDIT). Participants in both groups will be asked to complete these outcome measures at baseline, after 25-weeks post-treatment and then again after at a 12-week follow-up. The ITQ will be also completed by the ESTAIR group at the end of every module. In addition, data will be recorded on retention and DNA rate. The research assistant will be masked to group allocation to demonstrate to future funders this is achievable in a future trial.

**Note:** The ITQ will be completed by the therapist and participant at the end of every model. Due to feasibility concerns, the research assistant will not be masked to group allocation when collected measures at baseline, post-treatment, and follow-up. This is not expected to have any impact on outcomes as all primary and secondary outcome measures are self-report.

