### **Participant Withdrawal or Discontinuation**

Participants are free to withdraw from the study at any point, without giving any reason and without their legal rights or usual care being affected. Investigators may also withdraw participants if they deem their continuation to be harmful. The trial management group will review all instances of adverse events, whether they are judged to be attributable to the trial or interventions, and, based on this information, determine whether the participant should be withdrawn. Non-identifiable data from participants who have been withdrawn will be used to assess the feasibility of the study.

Participant engagement may be discontinued based on adverse events. In the instance of an adverse event, the clinician will inform the trial management group. The trial management group will review this form and determine whether the event could reasonably be attributed to the intervention or participation in the trial. The trial management group will review all instances of adverse events, whether or not they are judged to be attributable to the trial or interventions, and, based on this information, determine whether the participant should be withdrawn and/or whether the trial should be suspended, stopped or continued.

**Update note:** In addition to informing the study's trial management group, a protocol has been developed to appropriately address any concerns regarding the client's safety. The protocol involves informing and seeking supervision from Combat Stress' senior clinical staff and safeguarding leads, liaising with the client's GP, and potential involvement of local crisis teams if necessary. Any identified adverse events or concerns regarding risk will also be brought to the attention of Combat Stress' MDT team for relevant input.

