### **Study Suspension or Discontinuation**

The research project would be stopped in the event of several therapy-attributable adverse events. Any serious adverse events will be passed on to trial management group for review, who would have responsibility for assessing whether they are attributable to study participation, setting the threshold for discontinuation and issuing advice to suspend or discontinue. This advice would be acted upon by the researchers, in consultation with the Sponsor.

ESTAIR participants will continue treatment until (1) the clinical aims have been met, where the clinician deems 'reliable recovery' has occurred, or (2) the criteria for withdrawal have been met (4 or more missed sessions).

**Update note:** The criteria for withdrawal has been extended to include if participants do not attend 4 or more sessions in total or two continuous sessions, in the absence of any exceptional circumstances.

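### Non-severe adverse events have no usable TAU rate, and ITQ worsening is checked on 5 or 6 occasions in ESTAIR against 2 in TAU, so any-occasion counts are not comparable between arms

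*Combined protocol and SAP*

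**What the plan says.** **Non-severe events.** The Adverse Events section says "The AEQ used in the present study consists of 25 items". It then says "Non-severe adverse events will be defined as a score of" 3 or more on any item, and gives no other definition. The completer form is assigned by arm: "All participants completing the ESTAIR intervention will complete the trial-completer, patient-rated version of the AEQ". The early-withdrawal form is not: "participants who withdraw from the study will be asked to complete the early-withdrawal version of the AEQ together with the therapist". The same section describes the adverse-event assessment as something "which will be completed at end of treatment and at follow-up", without naming an arm.

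**Serious events.** Criteria (i) to (iii) are suicide-related. Criterion (iv) is a rise of at least 2 SD on the ITQ. None of the four is restricted by arm, and (iv) is not restricted to particular ITQ occasions.

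**When the ITQ is taken.** Under Outcome Measures, both arms complete it at baseline, at 25 weeks and at the 12-week follow-up. There is an addition for one arm: "The ITQ will be also completed by the ESTAIR group at the end of every module".

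**How events are reported and used.** Under Participant Withdrawal or Discontinuation: "In the instance of an adverse event, the clinician will inform the trial management group". Under Study Suspension or Discontinuation: "The research project would be stopped in the event of several therapy-attributable adverse events".

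**Analysis.** The Data analysis section covers recruitment and retention, the ITQ and secondary outcomes, and qualitative data. It contains no adverse-event analysis.

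**The concern.** A randomised pilot offers a concurrent control group against which harms can be read. The plan does not use it for non-severe events. A TAU participant who stays in the study never receives the form that defines such an event. The definition is also sensitive, because one raised item out of 25 makes a participant a case, in a population already in considerable distress. An ESTAIR rate of, say, 30% could be background or could reflect the therapy, and the data collected could not separate the two.

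For criterion (iv) the difficulty is unequal looking. If every ITQ counts, ESTAIR participants have more chances to cross the threshold by measurement variation alone, and a simple table by arm would lean against ESTAIR. Reporting through the clinician adds to the imbalance: ESTAIR involves up to 25 individual sessions, while the update note for TAU lists only a mental health assessment.

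The trial management group judges attribution and may suspend or stop the trial. The Study Design section also says the pilot rehearses the design of a larger trial, so the imbalance could be carried forward.

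**Working it through.** The plan states no expected adverse-event rate and no reference SD for criterion (iv), so there is no figure of its own to reproduce. The check is a tabulation, followed by illustrations under assumed inputs.

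**1. What is measured, by arm**

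| Measure | ESTAIR | TAU |
|---|---|---|
| Completer AEQ | Yes | Not assigned |
| Early-withdrawal AEQ | Yes, with therapist | Not excluded, but a study therapist is described only for ESTAIR |
| Serious events (i)–(iii) | Yes | Yes |
| ITQ at 25 weeks and follow-up | 2 | 2 |
| ITQ at module ends | 4 | 0 |

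Post-baseline ITQ occasions in ESTAIR: 4 + 2 = 6 if the fourth module end and the 25-week visit are separate, or 5 if they coincide. The Phase 1 model supports 5: it has five ITQ periods including baseline, the last labelled 25, which gives 4 post-baseline, plus follow-up. TAU has 2.

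**2. Background rate on the AEQ definition**

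Let p be the chance that one item reaches 3 or more with no therapy harm (assumed). For independent items, P(any of 25) = 1 − (1 − p)^25. For correlated items, a one-factor normal model was simulated with each item cut at its upper p-quantile.

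| p | Independent | Latent correlation 0.3 | Latent correlation 0.5 |
|---|---|---|---|
| 1% | 22% | 16% | 12% |
| 2% | 40% | 27% | 20% |
| 5% | 72% | 49% | 37% |

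The correlated columns are the more realistic, since these are items on one scale answered by one person. At latent correlation 0.5, with 30 participants, that is 30 × 0.121 = 3.6 to 30 × 0.372 = 11.2 people flagged without therapy harm.

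**3. False flags on criterion (iv)**

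Assume normal scores, no true change, a rise measured from baseline in baseline-SD units, and equal correlation r between any two occasions. All changes share the same baseline, so they are not independent. For one occasion the change has SD √(2(1 − r)), so P(rise ≥ 2) = 1 − Φ(2/√(2(1 − r))). At r = 0.5 this is 1 − Φ(2) = 2.3%, which agrees with the simulated 2.25%. Results for any occasion (1,000,000 draws):

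| r | 2 occasions | 5 occasions | 6 occasions |
|---|---|---|---|
| 0.4 | 6.1% | 11.9% | 13.5% |
| 0.5 | 4.1% | 8.4% | 9.5% |
| 0.6 | 2.3% | 4.9% | 5.7% |
| 0.7 | 1.0% | 2.1% | 2.4% |
| 0.8 | 0.2% | 0.4% | 0.4% |

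The ratio of 5 occasions to 2 is about 2 throughout (at r = 0.5, 8.4/4.1 = 2.0). In people, at r = 0.5: 30 × 0.0839 = 2.5 against 30 × 0.0412 = 1.2. High baseline scores would lower the figures in both arms, because the scale has a ceiling.

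**4. What a comparison would deliver**

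The 95% half-width for a difference in AEQ-event rates is 1.96 × √(2p(1 − p)/n), where p is now the participant-level rate, assumed equal in both arms. With n = 30: p = 0.2 gives 0.202; p = 0.4 or 0.6 gives 0.248. With n = 23 (75% of 30 is 22.5): 0.231 and 0.283.

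**The case against.** The strongest reply is that the plan does not depend on a between-arm rate. The management group reviews events case by case for attribution, no adverse-event test is planned, and a biased table is therefore hypothetical. That is fair as far as it goes. But the plan contains no adverse-event analysis at all, so nothing prevents any-occasion counts from being tabulated by arm, and judging attribution without a background rate is harder.

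A second reply is that the statement of timing names no arm, so TAU may be meant to complete the AEQ too. The assignment that follows names only ESTAIR completers, and nothing elsewhere gives the form to TAU. If both arms are intended, the text needs to say so.

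A third is that the AEQ may not suit TAU. The reference list gives it a title about psychological therapy, and only three example items out of 25 are shown. Those three (deterioration in mental state, stigma, more medication) could occur in either arm. How many of the other 22 could be shared is unknown, and this stands as a limit on the remedy.

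The protocol also commits to low questionnaire burden and essential data only. That is a real cost, though a small one, and the Adverse Events section itself aims to improve how adverse effects are recorded.

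A reader might infer that ESTAIR adverse-event rates have no control rate of any kind and cannot be interpreted. The documents do not support that. Serious events (i) to (iii) apply to both arms. Criterion (iv) can be computed in TAU at 25 weeks and follow-up. The early-withdrawal AEQ is not worded as ESTAIR-only. ESTAIR rates can still be described.

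**Conclusion.** The point holds for two specific quantities. Non-severe events, as defined, have no usable TAU comparator, so an ESTAIR rate cannot be separated from background. Any-occasion counts of criterion (iv) are not comparable between arms, because ESTAIR has 5 or 6 chances to TAU's 2. It does not extend to serious events (i) to (iii), nor to criterion (iv) at the two shared visits.

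The absence of a TAU form and the unequal occasions are read directly from the plan. The sizes are illustrative. They rest on assumed item rates of 1% to 5%, assumed latent correlations of 0 to 0.5, and assumed ITQ correlations of 0.4 to 0.8 with normal scores and no ceiling. The doubling for criterion (iv) is stable across that range, but the absolute excess is not: from about 6 percentage points at r = 0.4 to 0.2 at r = 0.8. This is a cheap improvement to a feasibility pilot and does not undermine its recruitment or retention aims.

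**What to change.** - Give the patient-rated AEQ to every randomised participant in both arms at the existing 25-week and 12-week follow-up contacts. For TAU, leave out items that refer only to the study therapy, and list in advance which items are shared.
- Add a short adverse-event paragraph to the Data analysis section: numbers and percentages by arm on the shared items, with a confidence interval for the difference and no test.
- Compare criterion (iv) between arms only on the 25-week and follow-up ITQs, and state the reference SD and the reference occasion. List ESTAIR module-end exceedances separately. This governs the comparison only and leaves safety review of individual events as the plan has it.

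The occasions then match, 2 against 2. The cost is one 25-item form, or fewer items, for about 30 TAU participants at two contacts that the research assistant already makes, plus the wording. The comparison stays descriptive: the 95% half-width is about 20 to 25 percentage points with 30 per arm, and about 23 to 28 with 23 per arm.

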## STUDY INTERVENTIONS

### **Enhanced Skills Training in Affective and Interpersonal Regulation (ESTAIR) (Cloitre et al., 2019)**

ESTAIR will be offered according to the protocol (Cloitre et al., 2019) by an experienced psychotherapist appointed for the study and trained to its delivery. Treatment sessions will be conducted individually. ESTAIR will consist of up to 25 sessions organised in 4 modules of about 6 sessions each tackling the symptoms of PTSD and DSO symptoms. The first initial session is a formulation session to link present difficulties and traumatic life events, discuss current issues and concerns, and collaboratively agree on relevant treatment goals.

ESTAIR entails a flexible application of tools that match participants' specific needs. The PTSD module provides narrative exposure to the traumatic memories and targets re-experiencing, avoidance, and hyperarousal symptoms. The AD module focuses on identifying and labelling feelings, emotion management, distress tolerance, and acceptance of feelings and experiencing positive emotions. The NSC module focuses on how to stay in the present moment and combat dissociation; self-compassion and mindfulness skills; challenging thinking patterns and developing a balanced view of self. The DR module focuses on exploration and revision of maladaptive schemas; effective assertiveness; awareness of social context; and flexibility in interpersonal expectations and behaviours that are displayed in social interactions.

**Update Note:** During the training of the psychotherapist in the ESTAIR intervention, slight modifications to the treatment protocol were made.

1. Given the pilot nature of the present study, it was determined that the modules would be delivered in a sequential manner, starting with the AD module, the DR module, the NSC module, and then finishing with the PTSD module if necessary.
2. It was determined that the ESTAIR protocol still consists of up to 25 sessions, starting with the initial formulation session and ending with the final summary and

relapse-prevention session. However, the number of sessions per module were modified from up to 6 sessions per module, to up to 5, 6, 5 and 7 sessions for the AD, DR, NSC and PTSD modules, respectively.

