## **Qualitative outcomes**

Qualitative data will be collected to explore the acceptability of the ESTAIR intervention. It was initially intended to invite a total of 4 completers and 4 non-completers from the ESTAIR arm to participate in a one-off qualitative interview. In order to enhance understanding of the acceptability of ESTAIR and to manage feasibility concerns, it was decided that all participants in the ESTAIR arm would be asked to answer specific, brief questions assessing their experience of the protocol, their perception of treatment in general, and suggestions for improvement.

**Update Note:** Given concerns that the specific questions administered to all participants completing the ESTAIR intervention would not provide rich enough data to infer the acceptability of the ESTAIR protocol, two safeguards are put in place for collecting qualitative data. Prior to completing the self-report qualitative questions, the research assistant will call participants to explain purpose of the qualitative items and will explain that responses will be anonymised by participant number and that they will not be shared with the therapist. If at the end of collection of qualitative data, responses do not appear rich enough to answer research questions 3 and 4, efforts will be made to recruit an independent research assistant/assistant psychologist to administer the one-off interviews to 4 completers and 4 non-completers from the ESTAIR arm. This will be done by an independent research assistant/assistant psychologist to reduce biases in interview responses, should they be required.

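### ESTAIR participants who withdraw complete the adverse-effects questionnaire with the therapist it rates, which may under-record non-severe adverse events and makes withdrawers hard to compare with completers

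*Combined protocol and SAP*

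**What the plan says.** The Adverse Events section sets two modes of collection. For completers: "All participants completing the ESTAIR intervention will complete the trial-completer, patient-rated version of the AEQ". For those who leave, with the stated aim of better adverse-event reporting: "participants who withdraw from the study will be asked to complete the early-withdrawal version of the AEQ together with the therapist". No Update Note changes either sentence. The section on ESTAIR says the treatment is delivered "by an experienced psychotherapist appointed for the study and trained to its delivery", and Treatment Fidelity also refers to a single therapist. For an ESTAIR withdrawer, the therapist in the AEQ sentence is therefore naturally read as that person's own.

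The AEQ matters because the same section uses it as the only definition of a non-severe event: "Non-severe adverse events will be defined as a score of" 3 or more on any item. Under Participant Withdrawal or Discontinuation, adverse events reach the trial management group through the clinician. The group's review bears on whether the trial continues.

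Qualitative outcomes treats acceptability data differently. Before answering the written questions, participants are told that "responses will be anonymised by participant number and that they will not be shared with the therapist". If interviews of completers and non-completers prove necessary, "This will be done by an independent research assistant/assistant psychologist to reduce biases in interview responses". Nothing equivalent is stated for the early-withdrawal AEQ.

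**The concern.** Someone leaving a therapy is asked to say, alongside the person who delivered it, whether it harmed them. Some may soften or omit an answer. Others may not take part at all: the Update Note under Study Suspension or Discontinuation makes four missed sessions in total, or two in a row, a ground for withdrawal, so some withdrawers will already have stopped seeing the therapist.

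Two things are at stake. The first is the number of non-severe adverse events recorded among withdrawers, which a pilot should measure well before a larger trial. The second is interpretation. The protocol's Update Note on defined completers shows that the investigators want to separate drop-out caused by treatment from drop-out with other causes. AEQ data from withdrawers would help with that, but less so if the mode of collection differs from that used for completers.

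**Working it through.** The plan gives no expected withdrawal rate, adverse-event rate or disclosure rate, so it has no figure to reproduce. The check has two parts.

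**Reading the sections together.**

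1. Completers: patient-rated form, no therapist involvement stated.
2. Withdrawers: a separate early-withdrawal form, completed jointly with the therapist.
3. Acceptability answers: withheld from the therapist; any interviews done by someone independent, with bias given as the reason.
4. The withdrawal AEQ has no self-completion option, no independent collector and no statement about what the therapist sees. The sentence does not say who the therapist would be for a withdrawer from the usual-treatment arm, so this point is confined to ESTAIR.

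**Illustration of size.** From the documents: n = 30 per arm (Sample size). The progression criterion requires 25-week ITQ data from at least 75% of those randomised, so 0.25 × 30 = 7.5 per arm could lack it if losses are equal. I use w = 7 withdrawals as a scale only, since missing ITQ data and withdrawal are not the same thing. Everything else is assumed:

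- p_c = 20%: share of completers with at least one AEQ item scored 3 or more.
- p_w = 50%: the same share among withdrawers.
- s: share of affected withdrawers who disclose with the therapist present, set at 70%, 50% or 30%. Full disclosure is s = 1.

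Recorded rate among withdrawers = p_w × s.

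Recorded rate in the arm = [(n − w) × p_c + w × p_w × s] / n.

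Chance that no withdrawer is recorded with an event = (1 − p_w × s)^w.

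| s | Withdrawers | Whole arm | Chance of none recorded among withdrawers |
|---|---|---|---|
| 1 | 50% | (4.6 + 3.5)/30 = 27.0% | 0.50^7 = 0.8% |
| 0.7 | 35% | (4.6 + 2.45)/30 = 23.5% | 0.65^7 = 4.9% |
| 0.5 | 25% | (4.6 + 1.75)/30 = 21.2% | 0.75^7 = 13.3% |
| 0.3 | 15% | (4.6 + 1.05)/30 = 18.8% | 0.85^7 = 32.1% |

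Varying w with the same p_c and p_w, for s from 0.7 down to 0.3:

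- w = 3: the arm rate falls from 23.0% to between 21.5% and 19.5%.
- w = 9: it falls from 29.0% to between 24.5% and 18.5%.

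If withdrawers are no more affected than completers (20% each, w = 7), the arm rate falls from 20.0% to between 18.6% and 16.7%.

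The direction follows from assuming s below 1; the calculation does not prove it. What it shows is proportion: a modest shift for the whole arm and a large one among withdrawers. At s = 0.3 the comparison reverses, with withdrawers at 15% against 20% in completers although the assumed truth is 50%.

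**The case against.** The protocol introduces joint completion in order to improve reporting, and a skilled therapist might draw out answers, or obtain forms, that a posted questionnaire would not. This stands as a possibility, and the documents offer no evidence either way. In the terms above, if a share r of affected withdrawers return a self-completed form and all of those disclose, self-completion records fewer events than fully attended joint completion whenever r is below s. The remedy therefore needs active follow-up.

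The contrast with the qualitative data can also be pressed too far. Those safeguards were added because answers might not be rich enough, and the independent interviewer is conditional. They are not a general rule about what therapists may see. They do show that the protocol accepts the principle of limiting response bias.

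A flat promise to keep answers from the therapist would cut across the route by which the clinician informs the trial management group. That objection is sound, and the fix has to deal with it. Nor is the existing research assistant clearly independent in the protocol's sense: the assistant is embedded in the clinical team and unmasked, and any interviews would call for a separate recruit. This favours self-completion over an interview by the assistant.

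Finally, the completer and early-withdrawal forms are already different versions, and Data analysis specifies no pooled AEQ analysis. Changing who is present would not by itself make the rates interchangeable. The questionnaire is cited as unpublished, so the intended mode of the withdrawal form cannot be checked.

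**Conclusion.** The point holds as a cheap improvement. Joint completion with the therapist may under-record AEQ-defined non-severe events among ESTAIR withdrawers, may add non-response, and makes their AEQ rates hard to set beside those of completers. The effect could be substantial among withdrawers and modest for the arm, but every figure for it rests on assumed withdrawal, event and disclosure rates.

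A reader might infer three stronger things that the documents do not support:

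- **That withdrawers are the people most harmed.** The protocol itself allows for drop-out unrelated to treatment, and missed sessions are a route to withdrawal. The concern does not need this claim.
- **That suppression is likely.** It is plausible, but nothing in the documents measures it.
- **That monitoring of serious harm is compromised.** Serious events (suicide, attempted suicide, suicidal crisis, or ITQ worsening of at least 2 standard deviations) are defined without the AEQ. What may be affected is the non-severe count, so far as it contributes to the trial-level review.

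**What to change.** 1. Have the early-withdrawal AEQ self-completed, by post or online. The research assistant sends it, follows it up and helps where needed.
2. Tell participants that answers are not shared with the therapist except where the existing procedures require it (Participant Withdrawal or Discontinuation; Management of disclosures).
3. Have the research assistant pass AEQ-defined adverse events to the trial management group, and reconcile Participant Withdrawal or Discontinuation, which now relies on the clinician to do this.
4. Record the therapist's own observations separately.
5. Report AEQ results for withdrawers and completers separately, with the mode of completion and the number of forms not returned.

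The cost is a little time from a research assistant who is already in post, contacts participants for outcome measures and is to be trained to respond to distress. There may be some unreturned forms. Small edits are needed in two sections, Adverse Events and Participant Withdrawal or Discontinuation, plus a line on AEQ reporting. Because this assistant is already unmasked, the change costs nothing in blinding.
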